10. HUMAN SUBJECTS

Population:

88 volunteers (Age 21 or over) will participate in this study. This includes a total of 55 ET subjects and 33 matched controls. Of these, 27 subjects have already completed participation and were enrolled at the University of Miami. Thus, 61 additional subjects will be enrolled at UCSD. Participants will be selected without regard to ethnicity or race.

Inclusion Criteria ET Patients:

- Age 21 or over
- Subjects willing to abstain from caffeine or alcohol for 48 hours prior to the fMRI scanning
- Diagnosis of Essential Tremor by a Movement Disorder specialist based on Tremor Research Group criteria

Age-matched Controls:

- Age 21 or over
- Absence of a primary neurological diagnosis

Exclusion criteria All Subjects:

- Abnormal findings on neurological exam consistent with an organic disorder
- Presence of a resting tremor on exam
- Pregnant, nursing, or suspected pregnancy
- Finding on the MRI safety questionnaire contraindicating MRI
- History of dementia, brain tumor, stroke, head trauma or a vascular malformation as obtained by history or from imaging studies
- History of a severe medical condition, such as cardiovascular disease, preventing subject from lying flat for up to 120 minutes
- Lacking the capacity to provide informed consent
- Claustrophobia or other restrictions that prevent subject from undergoing a scan in a confined space for up to 120 minutes
- Acute or chronic medications that influence hepatic metabolism or CNS function and cannot be temporarily discontinued for the length of the study
- Use of beta blocker medications for the management of hypertension

ET Patients:

- Movement frequency and severity preventing safe and effective MRI data collection
- Active or prior history of alcohol abuse or dependence
- Subject unwillingness to take a potentially intoxicating drug (ethanol)

- You do not have an accompanying adult who can provide transportation for you after consuming alcohol during one of the MRI visits
- You have an allergy to alcohol (ethanol)
- History of deep brain stimulation surgery or thalamotomy

Age-matched Controls:

• Use of a medication known to have tremor effects that cannot be temporarily tapered and discontinued (see below).

List of Medications with Known Tremor Activity:

Benzodiazepines (any)

Beta-blockers (any)

Carbemazepine

Gapapentin

Levetiracetam

Oxybate

Phenytoin

Primidone

Topiramate

Valproic acid

Zonisamide

PI will rely on self-reporting for inclusion/exclusion criteria. If PI has validity questions after informed consent is provided during the screening visit, medical records will be requested for further review.

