
After completion of the screening visit, subjects will be scheduled for the fMRI visit that will last no more than 2-hours. Subjects will be asked to lie still for up to 15 minutes at a time. An accelerometer device will be placed on the hand to measure movement. We will use fMRI to observe the brain's activity during three (3) different activities: arms resting by the side, right arm elevated and maintained in the air, and while drawing a spiral with the right hand. These tasks will be performed multiple times during 5-minute runs.

At the completion of study participation, subjects will receive payment for their participation. Payments for incomplete participation will be prorated based on consent form guidelines.

ET Volunteer Study Procedures

SCREENING

Subjects will be screened for eligibility and after providing informed consent, PI will conduct an examination to confirm the diagnosis of Essential Tremor (ET) and to exclude any other neurologic disorder. PI will obtain medical history, and a videotaped neurological exam that will include the following assessments: United Parkinson's Disease Rating Scale (UPDRS), Essential Tremor Rating Assessment (TETRAS), Montreal Cognitive Assessment (MOCA), Scale for the Assessment and Rating of Ataxia (SARA), baseline Spirography and Accelerometry. A urine pregnancy test will be performed on female participants of childbearing potential.

VIDEO RECORDING

As part of the evaluation, a video recording will be collected to document exam findings. Participants decide whether these videos may be used solely by the research team for this research project, or additionally may be used for other purposes such as educational or scientific meetings.

BLOOD SPECIMEN COLLECTION

As a part of the screening visit, participants will be requested to provide a blood sample that will be used for future genetic research on ET and related disorders. The total amount of blood removed will not exceed 20 ml (4 teaspoons).

MEDICATION TAPER

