A tremor medication consultation will be conducted with the PI reviewing the medication history. Participants taking no medications for ET will proceed to be randomized to one of the two fMRI visits (A or B). If a subject is on tremor medications and gives consent to participate in this study, tremor medications will need to be discontinued. This plan may be carried out by either the subject's primary physician or study PI in consultation with the Safety Advisory Committee (see section 14), depending on preference of subject and

treating physician. If subject has a treating physician, the PI will contact the physician to discuss whether there are any potential safety concerns with tapering tremor medications and review the plan to taper/titrate medications; taper will only occur with physician approval. The duration of the medication taper prior to MRI visit A depends on the type of tremor medication the subject is on with the period being at least five half-lives. In terms of the period between MRIs, this may be as short as two weeks and up to several months, though no explicit time limitations are set. The duration depends upon the time needed for a subject to taper off all tremor medications for MRI visit A, and the time necessary to reach a steady state of propranolol SR for MRI visit B. If a subject cannot tolerate the medication taper (e.g. worsening tremors create undo disability or the presence of an unexpected adverse effect), the PI will consult with the Safety Advisory Committee and discuss restarting medications with subject and treating physician (if present) and subject will be withdrawn from the study.

FUNCTIONAL MRI (FMRI) OVERVIEW

After completion of the screening visit, subjects will be scheduled for the fMRI visit that will also last approximately 2-hours. Women of childbearing potential will undergo a second urine pregnancy test prior to MRI visit A. ET participants already on stable doses of Propranolol SR will first undergo fMRI on Propranolol SR. Participants taking no medications for ET will be randomized to one of the two fMRI visits (A or B). After completion of one, participants will undergo the other visit type.

FMRI VISIT A

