During this visit, subjects will remain off tremor medications for a set period of time. The PI will provide specific instructions about how to do this since it varies based on the individual subject's medication history. Women of childbearing potential will undergo a second urine pregnancy test prior to MRI. During this visit, subject will be asked to perform three different activities: arms resting by the side, right arm elevated and maintained in the air, and while drawing a spiral with the right hand. Subject will perform these tasks multiple times during 5-minute runs. PI will then provide subject with a single 50-ml serving (1 shot) of 40% ethanol to drink and a high resolution structural MRI is performed, during which time the tremor suppression effects will begin. The same tasks performed during the first half of the study will be repeated. PI will complete an Alcohol intoxication Scale at the onset of the visit and again after MRI to ensure subjects are not intoxicated upon discharge. Subjects who demonstrate signs of intoxication will be monitored until they are back to their baselines.

FMRI VISIT B

During this visit, we will study how the brain and tremors respond to propranolol SR (Inderal LA). Before participating in this visit, subjects will need to be on a stable dose of this medication. In order to accomplish this, the subject will receive detailed instructions from PI on how to start and increase the medicine in consultation with the treating physician and/or Safety Advisory Committee. Subject responses to medication (benefits and adverse effects) will be monitored through weekly telephone calls. Once a stable dose of medication has been achieved, the subject will be scheduled for the fMRI scan. During this visit, the subject will be asked to perform three different activities: arms resting by the side, right arm elevated and maintained in the air, and while drawing a spiral with the right hand. At the completion of the visit, the study investigator will instruct the subject on how to taper off this medicine based on consultation with the treating physician and/or Safety Advisory Committee.

STUDY COMPLETION

Three (3) scenarios exist for study completion/termination:

1) Premature termination prior to completion of all visits

In this scenario, the subject will return to their baseline medications under the direction of their treating

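### The 48-hour caffeine and alcohol criterion is written for ET patients only, and no pre-scan intake record is described, so Aim 1 compares groups under different written pre-scan criteria

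*Combined protocol and SAP*

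**What the plan says.** In Section 10 (Human Subjects) the inclusion list for ET patients contains the item "Subjects willing to abstain from caffeine or alcohol for 48 hours prior to the fMRI scanning". The inclusion list for age-matched controls has two items: the same age limit, and "Absence of a primary neurological diagnosis". The section also has a block of exclusions for all subjects, and the abstinence item is not placed there.

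On verification, Section 10 says "PI will rely on self-reporting for inclusion/exclusion criteria".

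The healthy-volunteer fMRI procedures in Section 9 cover lying still ("Subjects will be asked to lie still for up to 15 minutes at a time"), the accelerometer and the three tasks. They do not mention caffeine or alcohol. For ET visit A, Section 9 says "PI will complete an Alcohol intoxication Scale at the onset of the visit", with a repeat after the scan.

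Aim 1 in Section 6 compares resting functional connectivity between the ET group and age-matched controls.

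On progress, Section 10 says "Of these, 27 subjects have already completed participation and were enrolled at the University of Miami" and "Thus, 61 additional subjects will be enrolled at UCSD".

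**The concern.** The sponsor treats recent caffeine and alcohol as worth controlling before a scan, but writes the rule for only one of the two groups that Aim 1 compares. If controls arrive with more recent caffeine or alcohol than ET subjects, and if that state affects resting connectivity, part of any group difference would reflect pre-scan intake rather than disease. The same mechanism could hide a real difference.

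The missing record makes this harder to resolve later. The ET item asks about willingness and eligibility rests on self-report, so adherence is not documented even among ET subjects. Without intake data in either group, nobody can check after the fact whether the groups were alike.

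**Working it through.** **1. Where caffeine and alcohol appear, by group**

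| Place | ET patients | Controls |
|---|---|---|
| Section 10, inclusion | Age, 48-hour abstinence item, ET diagnosis | Age, no primary neurological diagnosis |
| Section 10, exclusions for all subjects | Medication items; caffeine and alcohol not named | Same |
| Section 10, group-specific exclusions | History of alcohol abuse or dependence, unwillingness to take ethanol, ethanol allergy, and others; no 48-hour item | Tremor-active medication; the list names neither caffeine nor alcohol |
| Section 9, screening and fMRI procedures | Abstinence instruction not repeated | No abstinence instruction |
| Check or record before a scan | Intoxication scale at visit A | None described |

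Caffeine is mentioned once in the supplied text, in the ET inclusion list. The intoxication scale rates intoxication. It does not cover caffeine or the previous 48 hours, and it is not described for controls.

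**2. Which aim is affected**

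Aim 1 compares ET subjects with controls. Aims 2 and 3, as worded, compare tasks or drug conditions within ET subjects, all of whom fall under the same criterion. The asymmetry between groups therefore bears on Aim 1.

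**3. How many controls a change can still reach**

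Inputs from Section 8 (Progress Report): 22 ET subjects and 8 controls enrolled at Miami; 2 ET subjects and 1 control did not complete. Inputs from Section 10: targets of 55 ET subjects and 33 controls, 27 completed, 61 still to enrol.

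- Completed: 22 − 2 = 20 ET and 8 − 1 = 7 controls; 20 + 7 = 27, matching Section 10.
- Remaining: 55 − 20 = 35 ET and 33 − 7 = 26 controls; 35 + 26 = 61, matching Section 10.
- Share of controls still to enrol: 26/33 = 79%.

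**4. Size of the possible bias**

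The bias in a mean comparison is roughly the between-group difference in intake multiplied by the effect of intake on connectivity. The documents give neither quantity, and no SD, significance level, power or effect size for Aim 1. No figure can be derived.

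**5. Precision of a UCSD-only repeat of Aim 1**

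For a single scalar outcome, in SD units:

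- Full sample: SE = √(1/55 + 1/33) = 0.220.
- UCSD only: SE = √(1/35 + 1/26) = 0.259.
- Ratio: 0.259/0.220 = 1.18, so the standard error is about 18% wider.

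**6. What an intake table could show at UCSD**

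The 95% half-width for a group difference in the share reporting intake is 1.96 × √(p(1 − p)) × 0.259. The share p is an assumption: 5% gives ±11 percentage points, 10% gives ±15, 25% gives ±22 and 50% gives ±25.

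**The case against.** The strongest reply is that the evidence is only where one item is placed. It is a willingness criterion, no ET visit procedure turns it into a scan-day rule, and the removed consent pages may carry an instruction to controls. This stands as a limit: the point concerns the written criteria in the protocol text, not what subjects were told or did. A reader might infer that controls were in fact scanned with more caffeine or alcohol on board. The documents do not show that.

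A second reply is that the placement may be deliberate, since only ET subjects have a no-drug baseline followed by an ethanol challenge. That could account for the alcohol part. It does not account for caffeine, the item refers to fMRI scanning in general rather than to visit A, and it would leave the Aim 1 asymmetry in place.

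A third is that no passage says intake within 48 hours changes resting connectivity. This also stands, and it is why no size is claimed. A reader might reason from Aim 3, which hypothesises that ethanol reduces olivo-cerebellar connectivity, that recent alcohol in controls would favour the Aim 1 hypothesis. But that is an untested hypothesis about an acute dose in ET subjects, and nothing is said about the direction of a caffeine effect.

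A fourth is that moving the 48-hour item leaves another difference, because the exclusion for a history of alcohol abuse or dependence is also listed for ET patients only. This is correct. The change proposed here does not align every alcohol-related criterion.

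**Conclusion.** The point holds in a limited form. The abstinence criterion is written for ET patients only, the supplied text has no counterpart for controls, and no pre-scan intake record is described for either group. Followed as written, Aim 1 compares groups under different pre-scan criteria, which is an avoidable possible source of bias of unknown size and direction, possibly near zero.

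Two stronger readings are not supported:

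- A reader might turn the asymmetry into an inflated false-positive rate for Aim 1. Any such rate would be set entirely by an assumed bias, and a calculation for one scalar outcome would not cover the map-based analysis that is planned.
- A reader might extend the concern to Aim 3, since Section 9 says "In terms of the period between MRIs, this may be as short as two weeks and up to several months". The same ET criterion covers both visits, and nothing in the documents indicates that intake differs between them.

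The conclusion rests on the supplied protocol text and on the reading that only completers count towards the targets, which reproduces the protocol's own 27 and 61. It is a cheap improvement, of minor to should-fix severity.

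**What to change.** - In Section 10, apply the existing 48-hour item to all subjects, and add it to the healthy-volunteer fMRI instructions in Section 9. If the consent pages already instruct controls, say so in Section 10; the intake record would still be needed.
- Before every scan in both groups, record self-reported caffeine and alcohol intake over the previous 48 hours, and report it by group. The table will detect moderate to large imbalances only.
- Flag subjects scanned before the change, including any at UCSD.
- Optionally, repeat Aim 1 in UCSD subjects only (about 35 against 26) as a supplementary check. State that this changes site together with the abstinence rule, so it cannot isolate the effect of the rule, and that it is less precise than the full-sample analysis.

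The cost is one criterion moved, one instruction line, one short question per scan and a small inconvenience to control volunteers. No extra visit or procedure is needed.

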Aim 1. Does the cerebellum have increased blood flow and functional connectivity at rest? We will collect functional MRI (fMRI) data while participants are at rest and not experiencing tremor. Accelerometry will be used to confirm that no tremors occurred during data acquisition. We will utilize our Context Differential Autocorrelation Mapping (CDAM) method to compare global functional connectivity in a group of subjects with ET to a group of age-matched controls. We hypothesize that the inferior olive, cerebellum, and red nucleus (Mollaret's triangle) will have significantly greater functional connectivity in the ET group compared with controls.

Aim 2. Are postural and kinetic tremors associated with different aberrant networks? We will collect fMRI data while ET subjects perform two separate tasks. During one task, subjects will be verbally cued to elevate their arm in a tonic position to manifest postural tremor during fMRI data acquisition, in a block-design paradigm. Accelerometry will be used to quantify the frequency and severity of the postural tremor. During a second task, subjects will be similarly cued to draw an Archimedes spiral to elicit kinetic tremor. Tablet drawings will be digitized to quantify the frequency and severity of the kinetic tremor. We will use established fMRI analysis methods to generate statistical parametric maps (SPMs) and CDAM to compare the regional differences in activation and connectivity between postural and kinetic tremor. We hypothesize that postural tremor will be associated with greater inferior olive activation and connectivity, while kinetic tremor will have greater cerebellar activation and connectivity.

Aim 3. What regulatory changes in the tremor networks occur to explain the tremor-suppression effects of ethanol and propranolol? Using the resting, postural, and kinetic paradigms in Aims 1 and 2, we will assess the fMRI-based activation and connectivity changes for all ET subjects under three conditions: baseline (no drug), acute ethanol (50ml of 40%EtOH) challenge, and stable dose of propranolol. We will assess the regional activation and functional connectivity responses for each condition using SPM and CDAM methods. We hypothesize that ethanol's mechanism of tremor suppression is by reduction of olivo-cerebellar connectivity, while propranolol acts to reduce inferior olive activation.

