9. RESEARCH DESIGN AND METHODS

The study population will include patients diagnosed with essential tremor (ET) and healthy volunteers without a major neurological disorder based on inclusion/exclusion criteria described in section 10. All subjects will be recruited nationally with the aid of ET foundations and support groups, locally, and from the movement disorder clinic at UCSD. Every potential subject expressing interest in participating will undergo a telephone pre-screening to ensure they fulfill inclusion-exclusion criteria before being invited for the formal evaluation (screening visit). In order to balance the ethical conflicts of clinician and researcher, all potential participants will be provided with the informed consent form beforehand to review with their loved ones, thus eliminating the pressure to decide immediately whether to participate in study. Informed consent will be discussed with the subject by the study team. The informed consent phase will engage not only the subject but also the family members and/or friends and everyone involved is given the opportunity to ask questions and address concerns. Subjects providing informed consent will then be enrolled into the study.

Healthy Volunteer Study Procedures

SCREENING

After being screened for eligibility and providing informed consent, volunteers will have a thorough

examination that will lasts approximately 2-hours. PI will obtain medical history, and a videotaped neurological exam that includes the following assessments: United Parkinson's Disease Rating Scale (UPDRS), Essential Tremor Rating Assessment (TETRAS), Montreal Cognitive Assessment (MOCA), Scale for the Assessment and Rating of Ataxia (SARA), baseline Spirography and Accelerometry. If PI finds any non-ET abnormalities during the evaluation, the subject will be excluded and advised to consult their personal physician.

VIDEO RECORDING

As part of the evaluation, a video recording will be collected to document exam findings. Participants decide whether these videos may be used solely by the research team for this research project, or additionally may be used for other purposes such as educational or scientific meetings.

BLOOD SPECIMEN COLLECTION

As a part of the screening visit, participants will be asked permission to collect a blood sample that will be used as a control for future genetic research on ET and related disorders. The total amount of blood removed will not exceed 20 ml (4 teaspoons).

FUNCTIONAL MRI (FMRI)

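### The alcohol-history exclusion covers ET patients but not controls, so Aim 1 compares groups selected differently on alcohol history and may be confounded, in a direction the documents do not establish

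*Combined protocol and SAP*

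**What the plan says.** Section 10 (Human Subjects) has three exclusion lists: all subjects, ET patients, and age-matched controls. The criterion "Active or prior history of alcohol abuse or dependence" is in the ET list only, next to the items on willingness to drink ethanol, allergy to it and transport home.

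Controls must be 21 or over and meet "Absence of a primary neurological diagnosis". Their one specific exclusion concerns tremor-active medication that cannot be stopped. The all-subject list does not mention alcohol. Its nearest safeguard is "Abnormal findings on neurological exam consistent with an organic disorder".

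Section 9 adds a control screening visit of about two hours, with a medical history and several rating scales, including SARA for ataxia. It states: "If PI finds any non-ET abnormalities during the evaluation, the subject will be excluded". Section 10 also says "PI will rely on self-reporting for inclusion/exclusion criteria", with medical records requested only if validity is in doubt.

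Aim 1 in Section 6 will "compare global functional connectivity in a group of subjects with ET to a group of age-matched controls". It predicts greater connectivity in ET in the inferior olive, cerebellum and red nucleus. Age is the only matching factor named. Section 8 says controls are to be well matched but does not say on what. The text describes no adjustment for alcohol history.

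**The concern.** The criterion was probably written for the safety of the ethanol challenge, which only ET patients receive. It also acts as a selection rule in a between-group comparison. One group is screened on lifetime alcohol history and the other is not, so the groups can differ on that history for reasons unrelated to tremor.

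The regions matter. Aim 1 concerns the olivo-cerebellar system, and Aim 3 hypothesises that ethanol suppresses tremor by reducing connectivity there. The protocol therefore already treats alcohol as relevant to the quantity that Aim 1 measures. If a history of abuse or dependence alters resting connectivity in either direction, part of the observed ET-control difference would come from eligibility and not from disease.

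The point concerns lifetime history. The 48-hour caffeine and alcohol rule before scanning, which also appears only under ET inclusion, is a separate matter.

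**Working it through.** **1. Eligibility, side by side.** Take a person with past or current alcohol dependence, no neurological diagnosis and a normal examination.

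- As an ET candidate (that is, normal apart from tremor): excluded by the alcohol-history line in the ET list.
- As a control: meets both inclusion lines. The all-subject list has no alcohol item, the control exclusion concerns medication, and the Section 9 rule needs an abnormal finding. Eligible.

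The all-subject list already excludes on history alone for several brain conditions, such as stroke and head trauma. The plan therefore does not treat a normal examination as sufficient in general.

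**2. Counts in the documents.**

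- Section 10: 55 + 33 = 88 participants, and 88 − 27 = 61 still to enrol. Both stated figures reproduce.
- Section 8: 22 ET subjects and 8 controls were enrolled in Miami. Two ET subjects and one control did not complete, leaving 20 + 7 = 27.
- Controls still to scan: 33 − 7 = 26.

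**3. Size of a possible shift.** The documents give no test, alpha, SD or effect size for Aim 1, no share of controls with such a history and no effect of it. These inputs are assumed for illustration:

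- share of controls affected, f = 5% to 20%, or 33 × 0.05 = 1.7 to 33 × 0.20 = 6.6 people;
- connectivity lower by d = 0.5 to 1.0 SD in those controls;
- no affected ET patients, no true ET-control difference, two-sided alpha 0.05, normal approximation.

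Formulas, in SD units:

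- Shift in the control mean = f × d.
- SE of the difference = √(1/33 + 1/55) = 0.220.
- Critical difference = 1.96 × 0.220 = 0.432.
- Mixing affected and unaffected controls raises the control variance to 1 + f(1 − f)d², so the actual SE is s = √([1 + f(1 − f)d²]/33 + 1/55).
- Chance of a false ET > control result = P(Z > (0.432 − f × d)/s). Its nominal value is 2.5%.

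| f | d (SD) | Shift (SD) | Shift / SE | Chance of false ET > control |
|---|---|---|---|---|
| 5% | 0.5 | 0.025 | 0.11 | 3.3% |
| 5% | 1.0 | 0.05 | 0.23 | 4.4% |
| 10% | 0.5 | 0.05 | 0.23 | 4.3% |
| 10% | 1.0 | 0.10 | 0.45 | 7.1% |
| 20% | 0.5 | 0.10 | 0.45 | 6.8% |
| 20% | 1.0 | 0.20 | 0.91 | 15.8% |

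If the variance increase is ignored, the last entry is 14.6%.

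**4. The opposite sign.** If affected controls had connectivity 0.5 SD higher, the chance of a false ET > control result would fall to 1.5% at f = 10% and 0.9% at f = 20%. A true ET excess would then be understated by f × d, which is 0.05 and 0.10 SD.

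**5. Is any control likely to be affected?** At f = 5%, the chance that at least one of 33 controls has such a history is 1 − 0.95³³ = 82%. At f = 10% it is 97%. Among the 7 Miami completers the expected number is 7 × 0.05 = 0.35 to 7 × 0.20 = 1.4.

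**The case against.** The strongest reply is that the asymmetry has a sound reason and little consequence. Only ET patients drink ethanol, so only they need the exclusion for safety. Controls have a long examination that includes an ataxia scale, and any abnormality other than ET removes them. Those most likely to be affected are therefore largely screened out, which makes the upper end of the assumed 0.5 to 1.0 SD difference hard to defend. Every shift in the table is below one standard error, and every input behind it is assumed. All of this stands and limits the size of the point. It does not close the gap, because a history with a normal examination still passes.

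A reader might infer two stronger claims, and the documents support neither.

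- **That the gap pushes Aim 1 toward its hypothesis.** Aim 3 links ethanol to lower olivo-cerebellar connectivity, but that is a hypothesis about an acute dose in ET patients. No passage says what a lifetime history does to resting connectivity in a control.
- **That the ET group contributes no alcohol-related change.** The criterion stops at abuse or dependence, so heavier drinking below that threshold remains possible. It is checked by self-report, and Section 5 notes that many people with tremor get some relief from alcohol. Exposure in the ET group could offset part of any effect.

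**Conclusion.** The point holds as an avoidable, uncontrolled difference between the groups that may confound Aim 1. The asymmetry is certain from the text, but the direction and size of any bias are not. Under the assumed inputs the shift is 0.025 to 0.20 SD against a standard error of about 0.22 SD. If such a history lowers connectivity, the chance of a false ET excess rises from 2.5% to between 3.3% and 15.8%. If it raises connectivity, a true excess is masked. The higher figures need both a large affected share and a large difference in people who passed the examination. These calculations also put no affected patients in the ET group.

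Only comparisons with controls are affected. The within-ET contrasts in Aims 2 and 3 are not. The change is worth making because it is cheap and, by the Section 8 counts, about 26 of the 33 controls are still to be scanned.

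**What to change.** 1. In Section 10, move the alcohol abuse or dependence criterion from the ET list to the all-subject exclusions for the remaining UCSD enrolments.
2. Add the matching question to the control telephone pre-screen, which already exists (Sections 9 and 12).
3. For the 7 Miami controls who completed, take alcohol history from the screening record. Section 9 says a medical history is taken but not that it covers alcohol, so re-ask where it was not recorded.
4. Pre-specify a sensitivity analysis that repeats Aim 1 without any control who would have failed the criterion, and report it beside the main result.

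The cost is a short amendment, one question per control candidate, up to 7 follow-up contacts, and the loss of a few control volunteers from what Section 8 expects to be the easier recruitment stream. The planned 55 and 33 need not change. Dropping a Miami control would slightly reduce precision in the sensitivity analysis only. Self-report would still leave some misclassification, but the same rule would then apply to both groups.
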